Urine Pregnancy Test ⁸		X	X	X	
Vital Signs ⁹		X	X	X	
Height			X	X	
Physical Examination			X	X	
PHEX mutation analysis ¹⁰					
Anti-KRN23 antibody (ADA) ^{11,12}			X	X	

VISIT TYPE / NUMBER	HH ³ or TC ¹⁹ 27, 28, 29, 30, 31, 33, 34, 36, 37, 39, 40, 42, 43, 45, 46, and as applicable thereafter until 30 September 2018	HH ²⁰ 35, 41, and as applicable thereafter until 30 September 2018	32, 38, 44, and as applicable thereafter until 30 September 2018	EoT ²¹ visit number will vary for each subject	Safety Follow-up TC ²²
WEEK ⁴	Every 4 Weeks: 76, 80, 84, 88, 92, 100, 104, 112, 116, 124, 128, 136, 140, 148, 152, and as applicable thereafter until 30 September 2018	Every 12 Weeks: 108, 132 and as applicable thereafter until 30 September 2018	Every 24 Weeks: 96, 120, 144, and as applicable thereafter until 30 September 2018	Last visit occurring by 30 September 2018 ²¹	4 weeks (and, if applicable, 8 weeks) after EoT Visit ²²
Serum Phosphorus			X	X	
Serum Calcium			X	X	
Serum Creatinine			X	X	
Serum iPTH			X	X	
Serum FGF23 ¹²			X	X	
Serum 1,25(OH) ₂ D			X	X	
Bone Biomarkers ¹⁴			X	X	
ECHO, ECG			X	X	
BPI, SF-36 ¹⁵			X ¹⁵	X ¹⁵	
WOMAC ¹⁶					
6MWT, TUG					
X-Ray ¹⁷			X	X	
Interval History			X	X	
Serum KRN23 ^{12,18}			X	X	
Prior and Concomitant Medications	X	X	X	X	X

VISIT TYPE / NUMBER	HH ³ or TC ¹⁹ 27, 28, 29, 30, 31, 33, 34, 36, 37, 39, 40, 42, 43, 45, 46, and as applicable thereafter until 30 September 2018	HH ²⁰ 35, 41, and as applicable thereafter until 30 September 2018	32, 38, 44, and as applicable thereafter until 30 September 2018	EoT ²¹ visit number will vary for each subject	Safety Follow-up TC ²²
WEEK ⁴	Every 4 Weeks: 76, 80, 84, 88, 92, 100, 104, 112, 116, 124, 128, 136, 140, 148, 152, and as applicable thereafter until 30 September 2018	Every 12 Weeks: 108, 132 and as applicable thereafter until 30 September 2018	Every 24 Weeks: 96, 120, 144, and as applicable thereafter until 30 September 2018	Last visit occurring by 30 September 2018 ²¹	4 weeks (and, if applicable, 8 weeks) after EoT Visit ²²
Adverse Events	X	X	X	X	X
Weight			X	X	
Drug Administration ¹⁹	X	X	X		

Footnotes for Table 2.1 and Table 2.2

1,25(OH)₂D= 1,25-dihydroxy vitamin D; 6MWT = 6-minute walk test; ADA = anti-drug antibodies; BL = Baseline; ECG = electrocardiogram; ECHO = echocardiogram; EoT = end of treatment; FGF23 = fibroblast growth factor 23; HH = home health; HIV = human immunodeficiency virus; hr = hour; iPTH = intact parathyroid hormone; PHEX = phosphate regulating gene with homology to endopeptidases located on the X chromosome; Scr = Screening; TUG = timed up and go (test)

¹ Screening tests may be spread out over Screening and Baseline assessments, but have to be performed before drug administration. Screening and Baseline visits may be conducted on consecutive days but may be conducted up to 7 days apart.

² Baseline Visit tests and assessments may be spread out over 2 consecutive days to accommodate considerable number of assessments.

³ Home Health (HH) visits may also be conducted at the clinic depending on proximity of the subjects to the investigational site and local availability of home health resources.

⁴ The visit window for all visits after visit 3 and before EoT visit is is \pm 3 days. The visit window for the EoT visit is + 5 days.

⁵ Medical history to include review of previous test results for HIV antibody, hepatitis B surface antigen, and/or hepatitis C antibody. Viral testing will not be repeated in this study.

⁶ This comprehensive metabolic profile will include the standard Chem-20 serum panel (Na, K, Cl, bicarbonate, blood urea nitrogen [BUN], creatinine and creatinine clearance, glucose, alkaline phosphatase, alanine aminotransferase [ALT], aspartate aminotransferase [AST], gamma-glutamyl transferase [GGT], lactate dehydrogenase, phosphorus, uric acid, calcium, total protein, albumin, cholesterol and triglycerides, total bilirubin, and indirect bilirubin) as well as amylase and lipase.

⁷ Complete blood count, differential, and platelet count.

⁸ For women of childbearing potential only. A serum pregnancy test will be performed in the event of a positive or equivocal urine pregnancy result.

9 Vital sign measurements consist of seated systolic/diastolic BP measured in millimeters of mercury (mm Hg), HR (beats per min), respiration rate (breaths per min), and temperature in degrees Celsius (°C). Obtain at the beginning of each visit before any additional assessments are completed.

10 If the Baseline result for PHEX mutation analysis is negative or inconclusive (i.e., No Mutation, Likely Benign, Variant of Uncertain Significance, or Possibly Pathogenic), reflexive genetic testing will be performed (another blood draw may be needed) to assess additional genes associated with phenotypes overlapping with XLH.

11 If the development of anti-KRN23 antibodies is suspected in a given subject, samples may be obtained at additional time points on a case-by-case basis, if warranted.

12 If there is a technical or operational issue obtaining results for ADA, FGF23, or KRN23, then an additional blood sample may be obtained at the next suitable clinic visit.

13 Two serum samples should be collected at indicated clinic visits for serum phosphorus measurements. One sample will be read locally for determination of dosing decision; the other will be sent for analysis by the central laboratory.

14 Bone biomarkers will include serum measures of total serum ALP, bone-specific ALP (BALP), CTx, and P1NP.

15 Brief Pain Inventory (BPI) and SF-36 self-reported patient-reported outcomes (PROs) tools. These evaluations are not required past Week 144.

16 Western Ontario and McMaster Universities Osteoarthritis Index (WOMAC) self-reported PRO tool.

17 Standard radiographs will be customized by patient and will be repeated every 3 months or until specified fractures/psuedofractures are healed.

18 Sample collection for KRN23 assessment will begin at the earliest indicated study visit once necessary approvals have been obtained.

19 After proper training, subjects or their caregiver will administer study drug under the supervision of a healthcare provider. If the subject or caregiver demonstrates competency in administration of SC injections at that time, they will be instructed to perform future study drug administrations at home without supervision for HH visits occurring after week 96 or later (with the exception of site visits, during which subject/caregiver administration is preferable to demonstrate continued competency in technique, but not required). Drug administration by a HH nurse may continue at the discretion of the investigator, subject and/or caregiver. If the healthcare provider determines that the subject/caregiver requires additional training on SC injection technique, study drug will again be administered under the supervision of a healthcare provider at the next study visit. Once a subject or their caregiver has received appropriate SC injection technique training and begins administering study drug at home without supervision, they will be contacted via telephone by the study site every 28 days (+ 5 days), with the exception of site visits, to confirm administration of study drug and to record concomitant medications and AEs. Telephone visits may also be conducted at the clinical site depending on proximity of the subject to the site.

20 For subjects that are self-administering or having a caregiver administer study drug, a healthcare provider will return for HH visits occurring every 12 weeks after week 96 or visit 32 to assess vital signs, pregnancy, and record concomitant medications and AEs.

21 If a subject will be continuing KRN23 treatment under commercial use or another mechanism, the first dose of that treatment should not be administered until after completion of all of the EoT Visit assessments. Those subjects who terminate the study early will be asked to come back to the clinic for a final assessment. If the subject terminates the study early before Week 72, then the Week 72 assessments will be conducted. If the subject terminates the study early between Weeks 72 and EoT Visit (up until 30 September 2018, occurring within 4 weeks of last dose administration), then the EoT assessments will be conducted. Every reasonable effort should be made to have subjects return to the clinic for the final assessment.

22 To be completed for all subjects who complete the EoT Visit and are not immediately continuing KRN23 treatment under commercial use or another mechanism. The site personnel will initiate a Safety Follow-up telephone call (TC) 4 weeks (+ 5 days) after the EoT Visit to collect information on whether KRN23 treatment has been started through another mechanism and, if not, any ongoing or new AEs, serious adverse events (SAEs), or concomitant medications. Appropriate follow-up of AEs/SAEs should continue until all safety concerns, in the Investigator's opinion, are resolved. If the subject is not continuing KRN23 therapy under commercial use or another mechanism at that time, then site personnel will initiate a subsequent

Protocol Number: UX023-CL203
Amendment 2
29 September 2017

Safety Follow-up TC at 8 weeks (+ 5 days) after the EoT Visit to collect information on whether KRN23 treatment has been started through another mechanism and, if not, any ongoing or new AEs, SAEs, or concomitant medications.

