Primary Objectives

The primary objectives of this study are to:

- Assess the long-term safety of subcutaneous (SC) KRN23 administration in adult subjects with XLH
- Assess the proportion of subjects achieving serum phosphorus levels in the normal range (2.5-4.5 mg/dL) with long-term administration of KRN23
- Assess long-term PD of KRN23 as measured by changes in the following:
 - Serum and urinary phosphorus
 - Serum intact parathyroid hormone (iPTH)
 - Ratio of renal tubular maximum reabsorption rate of phosphate to glomerular filtration rate (TmP/GFR) and tubular reabsorption of phosphate (TRP)
 - Serum 1,25(OH)₂D
 - Serum FGF23
 - Bone biomarkers: serum alkaline phosphatase (ALP), bone-specific ALP (BALP), carboxy terminal cross-linked telopeptide of type I collagen (CTX), and procollagen type 1 N-terminal propeptide (P1NP)
- Assess long-term immunogenicity of KRN23 as measured by presence of anti-KRN23 antibody (anti-drug antibody [ADA])

Exploratory Efficacy Objectives

Exploratory efficacy objectives of this study are to:

- Evaluate changes in underlying skeletal disease as assessed by standard radiographs of the chest, lateral spine, right and left hand/wrist, right and left humerus, right and left radius/ulna, right and left femur/pelvis, right and left tibia/fibula, and right and left foot as well as any location(s) where the subject is currently experiencing tenderness or pain that may reflect underlying pathology, or where the subject has a history of recent (<3 months) fracture(s)
- Evaluate changes in patient-reported outcomes (PROs) and physical function including:
 - Patient reported pain - Brief Pain Inventory (BPI)
 - Disability - Western Ontario and McMaster Universities Osteoarthritis Index (WOMAC)
 - Quality of life (QOL) scores – 36-item Short Form Health Survey (SF-36)
 - Walking ability - 6-Minute Walk Test (6MWT)
 - Balance and agility - Timed Up and Go (TUG) Test
- Assess the long-term pharmacokinetic (PK) profile of KRN23

STUDY DESIGN AND METHODOLOGY:

Summary:

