Subjects will receive the initial SC injection of KRN23 at the clinic. Starting doses will be individual for each subject, i.e., the subject's last dose in study KRN23-INT-001 or KRN23-INT-002, either 0.3, 0.6, or 1.0 mg/kg. Up to Week 12, individual subjects who have not reached serum phosphorus levels above the lower limit of normal (LLN; 2.5 mg/dL) at the end of the dose interval may have their doses titrated upward every 4 weeks to a maximum dose of 1.0 mg/kg based on fasting trough serum phosphorus levels. Doses may be titrated downward if at any point the serum phosphorus level increases above the upper limit of normal (ULN; 4.5 mg/dL). KRN23 will be administered monthly (every 4 weeks), either at home or in the clinic. Subjects will return to the clinic monthly at Weeks 4, 8, and 12; then every 12 weeks at Weeks 24, 36, and 48; and then every 24 weeks at weeks 72, 96, 120, 144 and as applicable up until the End-of-Treatment (EoT) Visit, which will occur by 30 September 2018. Subjects may be seen at home by Home Health (HH) personnel between the clinic visits, or the HH visits may be completed in the clinic, depending on the proximity of the subjects to the investigational site and the location and availability of HH resources. After proper training, subjects may self-administer KRN23 or be administered KRN23 by caregivers without the supervision of HH nurse; in such cases, the HH visit would become a telephone visit.

Safety, immunogenicity, PK, PD, and efficacy assessments will be performed during the treatment period as outlined in the Schedule of Events. All assessments, with the exception of weight, will be repeated at the EoT Visit. Subjects may choose to withdraw from the study at any time.

NUMBER OF SUBJECTS PLANNED:

Twenty subjects will be enrolled in this study.

DIAGNOSIS AND CRITERIA FOR INCLUSION AND EXCLUSION:

INCLUSION CRITERIA:

Subjects eligible for enrollment in the study must meet all of the following criteria at Screening:

1. Have participated in KHK's KRN23-INT-001 or KRN23-INT-002 studies (received at least 2 doses of KRN23)
2. Estimated glomerular filtration rate (eGFR) ≥ 60 mL/min (using the Chronic Kidney Disease Epidemiology Collaboration [CKD-EPI] equation) or eGFR of 45 to <60 mL/min at Screening

with confirmation that the renal insufficiency is not due to nephrocalcinosis

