7.2 Discussion of Study Design, Including Choice of Control Group

This is an open-label study with the primary objectives of further characterizing the longterm- safety, immunogenicity, PK, PD, and efficacy profile of SC dosing of KRN23 every 4 weeks in adults with XLH. Efficacy assessments are included only as exploratory objectives; therefore, no control group is included. In a single-dose pharmacokinetic (PK) study of KRN23 administered SC, the time of maximum concentration (t_{max}) of KRN23 in serum ranged from 192 to 272 hours (8 to 11 days) after a single dose. KRN23 was eliminated with a half-life ($t_{1/2}$) of 322 to 448 hours (13 to 19 days). Exposure to KRN23 increased in a dose proportional manner up to 1.0 mg/kg following SC administration. Similar results in multiple-dose PK studies indicated that absorption of KRN23 following SC administration was consistent using a 4-week dosing schedule.

The design, dose, and dosing frequency of KRN23 in this open-label study were selected based on nonclinical data and data from completed clinical studies in which repeated doses of KRN23 up to 1.0 mg/kg were well tolerated by adult XLH subjects over a 48-week treatment period. The safety events to date have been mild to moderate in general, and only one drug-

related, life-threatening event of angioedema occurred in this study as described in Section 5.2.4. No immune response to KRN23 has been identified. While the safety is still under evaluation at this stage of development, the events to date suggest that KRN23 is well tolerated and that potential safety issues can be monitored.

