7.3.3.1 Stopping Rules

Individual subjects who experience any unexpected and possibly, probably, or definitely drug-related SAEs (Section 8.5.3) that represent a change in the nature or an increase in frequency of the serious event from their prior medical history will be assessed as to whether the subject will continue on the study. Likewise, if a subject experiences DLT (Section 7.5.3.13) or positive immunogenicity result(s), the case will be evaluated by the

investigator, medical monitor, and sponsor to determine the subject's continuation or withdrawal from the study.

Individual subjects will be monitored for ectopic mineralization by renal ultrasounds and ECHOs. If new or clinically significant worsening in mineralization is considered clinically meaningful by the investigator and/or sponsor and related to study drug, the subject will be discontinued from the study.

The Institutional Review Board (IRB) will be informed should unexpected and possibly, probably, or definitely drug-related SAEs occur. A full clinical evaluation of the event will be performed as described previously in order to make a decision regarding what actions to take, including whether to recommend stopping the study.

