7.5.2 Drug Concentration Measurements

To assess KRN23 concentration and possible accumulation, serum pre-dose levels will be evaluated as a PK parameter in this study. A pre-dose blood sample will be obtained at Weeks 24, 36, 48, 72, 96, 120, 144, and every 24 weeks as applicable through the EoT Visit or at the earliest indicated visit once the necessary approvals have been obtained. For each sample collection, the time elapsed since last study drug administration will be recorded on the eCRF.

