7.5.3.7 Anti-KRN23 Antibody Screening

To determine the immunogenicity profile of KRN23, blood samples will be obtained for analysis of ADA pre-dose at Weeks 0, 4, 12, 24, 36, 48, 72, 96, 120, 144, and every 24 weeks as applicable through the EoT Visit as indicated in [Table 2.1](#) and [Table 2.2](#). The concentration of anti-KRN23 antibodies in human serum will be determined using a validated sandwich enzyme-linked immunosorbent assay (ELISA) and a 2-tiered strategy: screening assay and specificity confirmation assay. If the development of anti-KRN23 antibodies is suspected in a given subject, samples may be obtained at additional time points on a case-by-case basis, if warranted.

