7.6.4 Determination of Sample Size

The rationale for the sample size for this open-label extension study is based on practical considerations to obtain the needed information to meet study objectives. The sample size of this study is based on the number of subjects who have satisfactorily completed studies KRN23-INT-001 and/or KRN23-INT-002, along with the other eligibility criteria, and have agreed to participate in this long-term extension study. Approximately 20 subjects may be

enrolled in this study. Subjects who were enrolled in the KRN23-INT002 bone substudy- and who received KRN23 are also eligible. Since this is an exploratory study, no formal statistical power and sample size estimation methods were used to determine the sample size; therefore, the current study design is not powered to assess a pre-defined statistical difference in any endpoint.

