### **8.6.2 Safety Lab Parameters**

The descriptive statistics will be provided for lab safety parameters (chemistry, hematology, and urinalysis parameters, GFR, HAHA). In addition, shift tables will be provided for HAHA (with categories Yes/No) and for amylase. For amylase, the following categories will be used:

- Normal
- Grade 1: 1 - 1.5 x ULR
- Grade 2: 1.5 – 2 x ULR
- Grade 3: 2 – 5 x ULR
- Grade 4: > 5 x ULR.

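### Negative anti-drug antibody results drawn while KRN23 is expected in serum are tabulated as Yes/No, with no rule for reading them against the drug level

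*Protocol*

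**What the plan says.** Protocol section 2 (Synopsis, Primary Objectives) lists as a primary objective: "Assess long-term immunogenicity of KRN23 as measured by presence of anti-KRN23 antibody (anti-drug antibody [ADA"]). Section 6 and SAP 2.1 also make long-term immunogenicity, measured by the presence of antibody, a primary objective. Protocol 7.6.1.1 turns it into a count of subjects who develop antibodies.

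- **Sampling.** Protocol 7.5.3.7 schedules ADA pre-dose at Weeks 0, 4, 12, 24, 36, 48, 72, 96, 120 and 144, then every 24 weeks through the End-of-Treatment (EoT) Visit.
- **Assay.** "The concentration of anti-KRN23 antibodies in human serum will be determined using a validated sandwich enzyme-linked immunosorbent assay (ELISA"), with a screening and a specificity-confirmation tier. No drug-tolerance limit is stated.
- **Dosing and follow-up.** Protocol 7.4.1 doses every 4 weeks until the visit before EoT. Section 7.1 makes the contacts after EoT telephone calls.
- **Half-life.** Protocol 7.2 gives a range "of 322 to 448 hours (13 to 19 days").
- **Reporting.** SAP 8.6.2, which uses the older term HAHA for ADA: "In addition, shift tables will be provided for HAHA (with categories Yes/No) and for amylase". Protocol 7.6.2.10 lists and summarizes the antibody data, including titers, by subject and population.
- **Drug levels.** Protocol 7.5.2: "A pre-dose blood sample will be obtained at Weeks 24, 36, 48, 72, 96, 120, 144", and then every 24 weeks through EoT. Protocol 7.6.2.7 plans summary statistics for these levels. Protocol 7.6.2.5 and SAP 8.8.1 allow an optional comparison with pharmacodynamic parameters. Nothing links them to ADA.

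**The concern.** Drug in a serum sample can compete for the antibody that an immunoassay is meant to detect. A negative is then informative only if the drug level lies within what the assay tolerates. A two-category table has no place for a negative that fails this condition, so it would presumably be entered as No alongside the sound ones.

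At stake is how a primary result is worded. Protocol 5.3 and 7.2 already describe earlier experience as showing no immunogenicity, without qualification, and a zero count here could be reported in the same way. The baseline sample is drug-free and the later ones are not, so even a Yes-to-No shift in the SAP table could reflect the change in drug level and not a loss of antibody.

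**Working it through.** **Inputs.** Half-life 322 to 448 h (protocol 7.2), which is 322/24 = 13.42 to 448/24 = 18.67 days; dosing every 28 days (7.4.1); ADA times (7.5.3.7); KRN23 times (7.5.2); planned sample: "Twenty subjects will be enrolled in this study" (synopsis).

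**The plan's own figure.** Protocol 7.5.3.11 equates 12 weeks with about 5 half-lives. 84/13.42 = 6.3 and 84/18.67 = 4.5. The range contains 5, so the figure is reproduced.

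**Expected residual drug.** The fraction of one dose left after t days is 2^(−t/half-life), assuming first-order elimination.

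| Days since dose | Half-life 13.42 d | Half-life 18.67 d |
|---|---|---|
| 25 | 27.5% | 39.5% |
| 28 | 23.5% | 35.4% |
| 31 | 20.2% | 31.6% |
| 56 (one skipped dose, 7.4.8) | 5.5% | 12.5% |
| 84 (no sample planned) | 1.3% | 4.4% |

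With repeated dosing, f = 2^(−28/half-life), and the steady-state trough is f/(1−f) of one dose: 0.235/0.765 = 31% to 0.354/0.646 = 55%. This is a bolus approximation.

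The EoT sample falls one dosing interval after the last dose, so it is in the same position. SAP 5.1 puts at least 21 months between earlier dosing and the first dose here, so Week 0 is effectively drug-free. It is the only such planned sample.

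**Which ADA samples have a same-visit drug level.** There are 9 post-baseline ADA times through Week 144, and 7 of them have a scheduled KRN23 sample. Weeks 4 and 12 do not. The protocol's summary of changes shows that KRN23 sampling was added by Amendment 1, dated 09 May 2016. Protocol 7.4.5 gives 156 to 184 weeks of treatment. Counting back from 30 September 2018:

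- first doses: about 22 March to 4 October 2015;
- Week 24: about 6 September 2015 to 20 March 2016, all before the amendment;
- Week 36: about 29 November 2015 to 12 June 2016, mostly before it.

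Week 24 is therefore probably unpaired, and so is most of Week 36. SAP Appendix 6 has no KRN23 row.

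**What a zero count can support.** The exact (Clopper-Pearson) two-sided 95% upper limit for 0 of n is 1 − 0.025^(1/n).

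| Subjects with a conclusive negative | Upper limit |
|---|---|
| 20 | 16.8% |
| 15 | 21.8% |
| 10 | 30.8% |
| 5 | 52.2% |

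The rows below 20 are illustrations. The documents give no basis for choosing among them.

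**The case against.** The strongest reply is that no harm has been demonstrated. The assay is described as validated and two-tiered, and its drug tolerance may be in a validation report outside these documents. If tolerance exceeds the trough level, every negative is sound. Pre-dose sampling is also the lowest-drug point of a regular dosing interval. Extra ADA samples are allowed if antibodies are suspected, and a repeat is allowed if a result cannot be obtained for technical reasons. Protocol 7.6.2.10 goes beyond Yes/No to titers, and hypersensitivity-type events are tracked separately in SAP 5.7. The study is descriptive: "no formal statistical power and sample size estimation methods were used to determine the sample size".

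Much of this stands. The residual fractions are expectations from a half-life, not measured levels, and what they represent depends on absorption. With a peak at 8 to 11 days (protocol 7.2), decline runs over only 17 to 20 days, leaving about 36 to 53% of the peak. No such fraction can be compared with a tolerance limit unless concentrations are known. That a negative is entered as No is inferred from the two-category table, not written out. None of this supplies a rule for interpreting a negative, and that gap remains.

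Two stronger readings are tempting. A reader might infer that antibodies are in fact being masked, but the documents contain neither of the two figures needed to show it. A reader might also note the provision in protocol 7.3.3.1 that, if a subject has "positive immunogenicity result(s), the case will be evaluated" for continuation or withdrawal, and infer that reclassifying results would strengthen that safeguard. It would not: the change acts at analysis, adds no sample and leaves that evaluation as it is.

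**Conclusion.** The point holds as a gap in how a primary result will be interpreted, not as evidence of false negatives. All scheduled post-baseline ADA samples are drawn with KRN23 expected in serum, no washout sample follows, and neither document says when a negative may be relied on.

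The number of affected results cannot be stated. It could be none if the assay tolerates trough levels. The 16.8% limit for 0 of 20 applies even without masking, and the wider limits show only how the statement weakens if fewer subjects have conclusive negatives.

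The conclusion rests on three assumptions: first-order elimination at the stated half-life, dosing close to schedule, and the general property that drug in the sample can reduce an immunoassay's sensitivity. Drug levels can help only where they exist, so the earliest visits cannot be rescued. This is a worthwhile, inexpensive improvement to a small exploratory study.

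**What to change.** In SAP 8.6.2 and protocol 7.6.2.10, state the validated assay's drug-tolerance limit and classify each on-treatment ADA result as:

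- **positive**;
- **negative**: assay negative, with same-visit KRN23 at or below the limit;
- **inconclusive**: assay negative, with KRN23 above the limit or with no paired level. This covers Weeks 4 and 12 and any visit before KRN23 sampling began.

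Report as the main figure the number of positive subjects over all treated subjects with ADA samples, with an exact 95% confidence interval. Beside it give the number with at least one conclusive negative and the number with only inconclusive results, so that the main figure is read as detected antibody.

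Incidence among conclusive subjects should be supplementary only. Positives from unpaired visits would count there, while subjects with only unpaired negatives would drop out, which can bias it upward. As a hypothetical case, take 1 positive, 9 conclusive negatives and 10 inconclusive subjects: the main figure is 1/20 = 5%, and the conclusive-only figure is 1/10 = 10%.

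The cost is SAP and protocol wording, one derived variable and the tolerance limit from the assay validation. No visit or sample is added. The SAP needs updating in any case, since it still follows the 2014 protocol and ends at Week 72. The downside is that some results now called negative will become inconclusive, so the immunogenicity statement will be somewhat less favourable.
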